## 9.2 Assessments of Adverse Events

Each adverse event will be assessed for severity, causality, seriousness and expectedness as described and outlined in the Sponsor SOPs documents stored on the NELFT R&D shared drive.

## 9.2.1 Severity

The generic categories below are given for use as a guide.

Category	Definition
Mild	The adverse event does not interfere with the participant's daily routine, and does not require further intervention; it causes slight discomfort
Moderate	The adverse event interferes with some aspects of the participant's routine, or requires further intervention, but is not damaging to health; it causes moderate discomfort
Severe	The adverse event results in alteration, discomfort or disability which is clearly damaging to health

# 9.2.2 Causality

The assessment of relationship of adverse events to the intervention is a clinical decision based on all available information at the time of the completion of the case report form.

If a differentiated causality assessment which includes other factors in the trial is deemed appropriate, please add/amend the following wording to specify:

It is of particular importance in this trial to capture events related to the procedure (Cognitive Stimulation Therapy) (refer to section 9.17 for reporting requirements). The assessment of relationship of an adverse event to this/these additional safety issue(s) will also be carried out as part of the trial.

The differentiated causality assessments will be captured in the trial specific CRF or SAE form (amend as required).

The following categories will be used to define the causality of the adverse event:

Category	Definition	
Definitely:	There is clear evidence to suggest a causal relationship, and other possible contributing factors can be ruled out.	
Probably:	There is evidence to suggest a causal relationship, and the influence of other factors is unlikely	
Possibly	There is some evidence to suggest a causal relationship (e.g. the event occurred within a reasonable time after administration of the trial intervention). However, the influence of other factors may have contributed to the event (e.g. the participant's clinical condition, other concomitant events).	
Unlikely	There is little evidence to suggest there is a causal relationship (e.g. the event did not occur within a reasonable time after administration of the trial intervention). There is another reasonable explanation for the event (e.g. the participant's clinical condition, other concomitant treatments).	
Not related	There is no evidence of any causal relationship.	
Not Assessable	Unable to assess on information available.	

# 9.2.3 Expectedness

Category Definition	
---------------------	--

Expected	An adverse event which is consistent with the information about the intervention listed in the SPC, manual of Operation (amend as appropriate) or clearly defined in this protocol.
Unexpected	An adverse event which is not consistent with the information about the intervention listed in the SPC, manual of Operation (amend as appropriate)* or clearly defined in this protocol.

\* This includes listed events that are more frequently reported or more severe than previously reported.

There are no known adverse effects of Cognitive Stimulation Therapy. However, taking part may possibly cause distress/ inconvenience for some participants with dementia

## 9.3 Recording adverse events

All adverse events will be recorded with clinical symptoms and accompanied with a simple, brief description of the event, including dates as appropriate.

All adverse events will be recorded in the CRF until the participant completes the trial.

# 9.4 Procedures for recording and reporting Serious Adverse Events

All serious adverse events will be recorded in the participant records hold in the Trust and the CRF, and the sponsor's AE log. The AE log of SAEs will be reported to the sponsor at least once or twice per year.

All SAEs (except those specified in section 9.5 as not requiring reporting to the Sponsor) must be recorded on a serious adverse event (SAE) form. The CI/PI or designated individual will complete the sponsor's SAE form and the form will be preferably emailed to the Sponsor within 5 working days of becoming aware of the event. The Chief or Principal Investigator will respond to any SAE queries raised by the sponsor as soon as possible.

Where the event is unexpected and thought to be related to the intervention, this must be reported by the Investigator to the Health Research Authority within 15 days.

## 9.5 Serious Adverse Events that do not require reporting (if applicable)

Not applicable

## 9.6 Unblinding (if applicable)

This is not relevant as the participants will be aware of the whether or not they are receiving the intervention. The research assistant administering the questionnaires will be blind to the treatment group.

## 9.7 Reporting Urgent Safety Measures

If any urgent safety measures are taken the CI/ PI shall immediately and in any event no later than 3 days from the date the measures are taken, give written notice to the relevant REC and Sponsor of the measures taken and the circumstances giving rise to those measures.

## 9.8 Notification of reportable protocol violations

A reportable protocol violation is a breach which is likely to effect to a significant degree:

(a) the safety or physical or mental integrity of the participants of the trial; or

(b) the scientific value of the trial.

The sponsor will be notified immediately of any case where the above definition applies during the trial conduct phase.

# 9.9 Reporting incidents involving a medical device(s) (if applicable)

Not applicable

## 9.10 Trust Incidents and Near Misses

An incident or near miss is any unintended or unexpected event that could have or did lead to harm, loss or damage that contains one or more of the following components:

a. It is an accident or other incident which results in injury or ill health.

b. It is contrary to specified or expected standard of patient care or service.

c. It places patients, staff members, visitors, contractors or members of the public at unnecessary risk.

d. It puts the Trust in an adverse position with potential loss of reputation.

e. It puts Trust property or assets in an adverse position or at risk.

Incidents and near misses must be reported to the Trust through DATIX as soon as the individual becomes aware of them.

A reportable incident is any unintended or unexpected event that could have or did lead to harm, loss or damage that contains one or more of the following components:

- a) It is an accident or other incident which results in injury or ill health.
- b) It is contrary to specified or expected standard of patient care or service.
- c) It places patients, staff members, visitors, contractors or members of the public at unnecessary risk.
- d) It puts the Trust in an adverse position with potential loss of reputation.
- e) It puts Trust property or assets in an adverse position or at risk of loss or damage.

#### 10 Data management

#### **10.1** Confidentiality

All data will be handled in accordance with the GDPR guidelines.

The Case Report Forms (CRFs) will not bear the participant's name or other personal identifiable data. The participant's initials, date of birth and trial identification number, will be used for identification and this will be clearly explained to the patient in the Patient information sheet. Patient consent for this will be sought.

## **10.2** Data collection tools and source document identification

Data will be collected from sites on trial specific case report forms (CRFs). The data will be anonymous and entered into the electronic data capture system, so that data can be extracted for statistical analysis.

Source data are contained in source documents and must be accurately transcribed on to the CRF. Examples of source documents are medical records which include laboratory and other clinical reports etc.

A source document list will be implemented prior to the start of the trial to identify:

- which data is to be recorded directly onto the CRF;
- which data is recorded firstly into source documents, such as medical notes, and then transcribed into the CRF; and
- which data is not to be recorded in the CRF but only recorded in source documents, e.g. participant questionnaires.

It is the responsibility of the investigator to ensure the accuracy of all data entered in the CRFs. The delegation log will identify all those personnel with responsibilities for data collection and handling, including those who have access to the trial database.

## **10.3** Completing Case Report Forms

All CRFs must be completed and signed by staff that are listed on the site staff delegation log and authorised by the CI/ PI to perform this duty. The CI/PI is responsible for the accuracy of all data reported in the CRF.

Once completed data from the CRFs will be entered into the electronic data capture system. The data can then be downloaded for data cleaning and statistical analysis. The original copies must remain at the sponsor site and securely stored. Source data verification of a CRF page should be completed and all data queries answered prior to submission where possible.

#### 10.4 Data handling

In the study, questionnaires (see section on pre-assessment and assessment measures) will be collected from patients in accordance with the patient consent form, patient information sheet and section 8 of this protocol.

The questionnaires will be appropriately kept at the Research and Development Department at North East London NHS Foundation Trust and the employed research assistant supervised by NELFT study PI will act as the data controller of such data for the study. Data will be entered into a database hosted on RedCap by the research assistant and may be downloaded by NWORTH electronically for data cleaning and statistical analysis. Any other data transferred to NWORTH will be encrypted, password protected and contain no identifiable data. A data management plan will be developed to describe procedures for data storage and data cleaning.

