#### 3. Feasibility Randomised Controlled Trial

This will be a single blind, pilot randomised controlled trial of CST delivered by professionals versus treatment as usual. Fifty participants will be randomised to either the intervention group or control group (treatment as usual). Randomisation will occur after baseline assessments are completed. Each arm will have 25 participants and they will be allocated to one CST group with up to five participants in each group.

The duration of the intervention will be 7 weeks. There will be assessments at baseline during the two weeks prior to randomisation, and at the end of the intervention after 8-9 weeks.

Please refer to figure 1 which shows the overall trial design.

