## 8.2 Randomisation Procedures

Randomisation will occur after eligibility, consent and baseline assessments have been carried out by the blinded research assistant. Randomisation will be undertaken by the coordinating trials unit (NWORTH) using a dynamic adaptive randomisation algorithm via a secure online interface. An unblinded member of the team will enter necessary details into the web based randomisation system. This system will randomly allocate the participant to either the intervention or control arm. Randomisation will be stratified for recruited NHS Trust site/centre. Participants will be randomly allocated to intervention group or control group and informed of group allocation by an unblinded member of the research team. Although participants cannot be blinded to their allocated group, the research assistant administering the questionnaires will be blinded to the allocation group. Due to the risk of carers revealing the allocation group, participants and their carers will be reminded before the follow-up assessments not to divulge this information. At the end of the study, we will assess researcher blindness by asking them to guess the allocated group.

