## 8.6 Discontinuation/withdrawal of participants

A participant may be withdrawn from trial whenever continued participation is no longer in the participant's best interests, but the reasons for doing so should be recorded. Reasons for discontinuing the trial may include:

- disease progression whilst in trial
- Chronic current illness
- patients withdrawing consent or Personal/Nominated Consultees withdrawing assent for participants lacking capacity

The decision of a participant to withdraw from treatment will be recorded in the CRF and medical notes. If a participant withdraws from the intervention, they will be asked to continue to provide follow up data. Their decisions regarding withdrawal from the intervention and withdrawal from follow-up will be recorded in their medical notes and in the trial CRF, along with any reasons that they have shared.

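### The assessor's allocation guess is collected too late to test blinding at the follow-up SIB, and the protocol does not keep the blinded assessor away from arm-revealing data entry

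*Protocol*

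**What the plan says.** Section 5 describes the design: "This will be a single blind, pilot randomised controlled trial of CST delivered by professionals versus treatment as usual". One role is blinded. Section 8.2 states that "the research assistant administering the questionnaires will be blinded to the allocation group", and 9.6 repeats it: "The research assistant administering the questionnaires will be blind to the treatment group". Section 1 lists one research assistant.

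The check on blinding is in 8.2: "At the end of the study, we will assess researcher blindness by asking them to guess the allocated group". The same section gives randomisation entry and the informing of participants to an unblinded team member, and has participants and carers reminded before follow-up not to reveal the arm.

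On data entry, 10.4 says "Data will be entered into a database hosted on RedCap by the research assistant". Section 10.3 says "Once completed data from the CRFs will be entered into the electronic data capture system", without naming who does it. On what the CRF holds, 8.6 says "Their decisions regarding withdrawal from the intervention and withdrawal from follow-up will be recorded in their medical notes and in the trial CRF", and asks those who stop the intervention to keep giving follow-up data. Section 9.2.2 adds "The differentiated causality assessments will be captured in the trial specific CRF or SAE form".

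**The concern.** There are two linked weaknesses.

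First, a guess is informative about the SIB only if it reflects what the assessor knew when giving the SIB. A guess taken at study end mixes that with forgetting and with anything learned later. Forgetting pulls guesses towards chance and makes blinding look better than it was. Later knowledge makes it look worse. The two cannot be separated afterwards.

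Second, the person who must stay blind is the only person named as entering data in REDCap, and the text sets no boundary around forms that reveal the arm.

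The Summary names cognitive functioning as the primary clinical outcome and plans to use its means and standard deviations to size a larger study; 11.1 adds effect estimates with 95% confidence intervals. There are two cognition measures. The other one, the DLD, is completed by carers, who can know the allocation. Whether assessor blinding can be kept is also something a feasibility trial is well placed to learn.

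**Working it through.** The protocol gives no figure on this point to reproduce. The check is a trace of roles and timing, with simple arithmetic.

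**1. Which measures depend on assessor blinding (table in 8.1).**
- Administered directly by the researcher: SIB (1).
- Completed by the carer: DLD, QOL-AD proxy, GDS-LD proxy, EQ-5D-5L proxy, modified CSRI (5).
- Rated by the participant: EQ-5D-5L (1).
- Total 1 + 5 + 1 = 7. Participants cannot be blinded and 8.2 recognises that carers may disclose the arm, so assessor blinding mainly protects 1 of 7.

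**2. How old the guesses would be.** Let R be the recruitment period and f the time from randomisation to follow-up (8-9 weeks, section 5), assumed equal for all. The first recruit is assessed at time f and the last at R + f. If guesses are collected once the last follow-up is done, the first recruit's guess is (R + f) − f = R old.
- Section 11.3 gives R = 10 to 15 months, so the gap is 10 to 15 months.
- At the planned four recruits a month, R = 50 / 4 = 12.5 months, so the gap is 12.5 months.
- With even recruitment the average gap is R / 2, that is 5 to 7.5 months.

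If guesses were collected later than the last follow-up, every gap would be longer.

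**3. What 'end of the study' means.** The control-group text in section 7 uses a different, participant-level phrase when it means the end of one person's involvement. The wording in 8.2 is therefore most naturally read as the end of the whole study. The same control-group text allows control participants to be offered the groups after follow-up, so information reaching the assessor later may not even reflect the randomised arm.

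**4. Data entry set beside CRF content.**

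| Item | Where held | Reveals the arm? | Who enters it |
|---|---|---|---|
| Outcome questionnaires | Paper, then online within 48 hours (8.1) | Not in themselves | The researcher |
| Withdrawal from the intervention | CRF (8.6) | Yes: only the CST arm has an intervention to leave | Not stated (10.3); possibly the research assistant (10.4) |
| Causality in relation to CST | CRF or SAE form (9.2.2) | Sometimes | Not stated |
| Attendance and engagement | CST participation forms (section 4) | Yes | Not stated |

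A withdrawal during the 7-week programme comes before the week 8-9 assessment. Because 8.6 keeps such people in follow-up, the participants whose CRF reveals the arm can be the ones the assessor must then test blind. The protocol does not reserve these forms for unblinded staff, restrict the assessor's access, or hold the entries back until follow-up is done.

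**5. Precision of the guess.** If half of the guesses were correct, the 95% Wilson interval would be about 37-63% for 50 guesses, or 35-65% for 38 (assuming roughly 75% of 50 are followed up). The check is coarse at any time, which is more reason not to weaken it further by delay.

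**The case against.** The strongest reply concerns 10.4. That section opens with the questionnaires, and the sentence after the one on REDCap entry speaks of any other data sent to the trials unit, which suggests that the assistant enters questionnaires only. Section 8.1 fits: the researcher brings the paper assessments back and enters them. Section 10.3 names no one for CRF entry, 9.4 gives SAE forms to an investigator or designee, 10.2 leaves database access to the delegation log, and 10.4 promises a data management plan. Role rights are often set in such documents. This stands to the extent that the narrow reading is possible and no passage says that the assistant keys arm-revealing forms or does so before follow-up. But the entry sentence itself carries no limit, and the plan is described as covering storage and cleaning, not blinding. Taken alone, this half of the point is close to missing detail.

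A reader might infer that expected 75% retention makes arm-revealing entries common, since 25% of 50 is about 12 people. It does not. Retention counts completion of the trial in both arms, and those lost have no follow-up SIB to bias. The relevant group is CST participants who stop the intervention but stay in follow-up, and the protocol gives no figure for it. Nor does a causality entry always reveal the arm: categories such as not related are possible in either arm, and 9.2.3 says that CST has no known adverse effects.

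Finally, no progression criterion rests on an SIB treatment effect and no hypothesis test is planned. That limits the consequence but does not remove it.

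**Conclusion.** The timing of the guess is a real defect in what the protocol fixes. Read at study level, it leaves guesses up to about 10 to 15 months old for the earliest recruits, and they cannot separate unblinding before the SIB from unblinding after it. This assumes that 8.2 means the end of the whole study, which its wording favours but does not make certain.

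The data-entry point is a risk without a stated safeguard, not a demonstrated breach. It rests on the unqualified wording of 10.4, the single research assistant listed, and the CRF record of intervention withdrawal among people kept in follow-up.

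A reader might go further and conclude that the single-blind claim fails, or that blinding cannot be verified at all. The documents do not support either. There are safeguards at randomisation and before follow-up visits, no passage shows the assessor seeing the arm before an SIB, and a check is planned, though a weak one. The change is worth making because it is nearly free and bears on the one measure that assessor blinding mainly protects.

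**What to change.** In 8.2, replace the study-end timing with this: immediately after each participant's follow-up assessment, the assessor records the guessed arm, the certainty of the guess and any disclosure of allocation. State that guesses will be reported by arm.

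In 10.4, state that the blinded research assistant enters only the outcome questionnaires. The existing unblinded team member enters the attendance, intervention-withdrawal, adverse-event and causality forms, and the assessor's REDCap role cannot open these until that participant's follow-up is complete.

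The cost is protocol wording, one extra form item, one role setting in REDCap and slightly more data entry for existing unblinded staff. No new post is needed.

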# **11** Statistical Considerations

#### **11.1 Statistical analysis**

Baseline characteristics will be summarized for all participants, the intervention group and control groups separately. Participants' uptake of and adherence to the intervention, as well as follow-up rates, will be summarized and presented as percentages.

Although determining differences in clinical outcomes between the arms is not the primary purpose of this trial, comparisons will be undertaken to investigate the feasibility of studying these outcomes and to calculate estimates for the likely effect sizes and 95% confidence intervals. As recommended in guidelines for good practice for the analysis of pilot studies, the focus of the results will be on the estimates of the treatment effects rather than statistical significance and as such no hypothesis testing will be undertaken. Differences between the two comparison groups will be presented in the form of an unadjusted mean difference for continuous outcomes, and an odds ratio for binary outcomes, with

their associated 95% confidence intervals. Despite the individual randomisation there is group based treatment and therefore consideration will also be made in regard to estimation of the potential intracluster correlation (ICC) coefficient. The estimation of the likely ICC will be able to guide the sample size of a future trial.

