# **11.2** Sample size calculation

This is a feasibility study with no formal power calculation. Instead, a sufficient number of participants need to be recruited in order to determine the attrition and recruitment rates and how these are related to feasibility for a full scale RCT. By setting our target sample size at 50 we will achieve adequate precision around our expected retention rate of 75% (95% confidence interval of 62-86%) to determine the feasibility going forward. Based on our previous study data we are anticipating we will have to screen a maximum of 70 people to reach our sample size.

There is no available data on the use of Cognitive Stimulation Therapy in the treatment of dementia in people with Learning disability. This sample should also provide adequate precision using a confidence interval approach which considers the likelihood of a future definitive study finding a relevant effect size.

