# 12.2 Quality of life (QOL) and quality-adjusted life years (QALYs)

The EQ-5D-5L is administered to all participants at baseline and at follow-up, to allow reporting of different domains of the participant's health-related quality of life (mobility, self-care, usual activities, pain/discomfort and anxiety/depression) and to see how this has changed in each of the two randomised groups, and to allow utility weights (also called QOL scores or values) to be

calculated from the responses to the EQ-5D-5L using standard algorithms. These QOL values, calculated from the EQ-5D-5L responses captured from participants at baseline and follow-up, are then used to calculate quality-adjusted life-years (QALYs) for participants over the time horizon of the study, using area under the curve methods. QALYs are calculated adjusting for baseline QOL values.

QALYs are the outcome preferred for use in cost-effectiveness analysis by the National Institute for Health and Care Excellence (NICE) when combined together with information on costs. The five questions covering the five domains listed above are followed by a visual analogue score on the second page of the questionnaire, which is not used in health economic analysis but is required to be included for valid administration of the questionnaire.

The feasibility study outcomes here will assess proportions of participants who return completed EQ-5D-5L questionnaires (focusing on the 5 items on the first page and considering the VAS responses separately) at the two timepoints.

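### Section 11.1 fixes an unadjusted mean difference although baseline scores are collected and randomisation is stratified by trust; this forgoes precision if baseline and follow-up are at least moderately correlated

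*Protocol*

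**What the plan says.** Protocol section 11.1 sets the form of the between-arm comparison: "Differences between the two comparison groups will be presented in the form of an unadjusted mean difference for continuous outcomes", with an odds ratio for binary outcomes, each given with "their associated 95% confidence intervals". The stated aim is "to calculate estimates for the likely effect sizes and 95% confidence intervals", and "as such no hypothesis testing will be undertaken". No adjusted estimate is mentioned for any clinical outcome.

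Three other places bear on this:

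- Section 8.1 has the outcome measures completed before randomisation and again in weeks 8 and 9, so a baseline value is planned for each.
- Section 8.2: "Randomisation will be stratified for recruited NHS Trust site/centre".
- Section 12.2, on the health economic outcome: "QALYs are calculated adjusting for baseline QOL values".

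The estimates have stated uses. The Summary (section 2) wants the mean and SD of cognitive functioning for the sample size of a larger study. Section 4 relies on the preliminary analysis to judge whether the measures respond to the intervention. Section 11.2 says the sample gives adequate precision for considering a relevant effect in a future trial, but gives no figure for that precision.

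**The concern.** A baseline score on the same scale is usually the strongest available predictor of the follow-up score, and here it costs nothing because it is already collected. Leaving it out of the estimate discards information in a trial expected to have about 38 people at follow-up. Trust is built into the randomisation but does not appear in the analysis.

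Because the protocol drops testing and puts the weight on estimates and intervals, the width of those intervals is what this part of the plan delivers. A wider interval gives a weaker basis for choosing the future primary outcome and for judging which effects remain plausible. If follow-up scores are compared, a chance difference between arms at baseline also passes in part into the estimated effect. The choice is written into the protocol, so it is not a detail left open for the SAP.

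**Working it through.** **The plan's own figure.** Section 11.2 states "This is a feasibility study with no formal power calculation", so there is no power figure to reproduce. Its one precision figure is the interval of 62-86% around 75% retention. With 37 of 50 retained, 0.74 ± 1.96 × sqrt(0.74 × 0.26 / 50) = 0.618 to 0.862, which agrees. That figure concerns retention, not the treatment effect.

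**Inputs.**
- Sample size 50 (section 11.2: "By setting our target sample size at 50"), 25 per arm (section 5).
- Retention 75% (section 11.2): 50 × 0.75 = 37.5, taken as 38, or 19 per arm.
- Trust terms: section 6.3 counts five trusts and the Summary lists six, so four or five terms.
- r, the correlation between baseline and follow-up: not in the protocol. It is an assumption, shown over a range.

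**Formulae**, in units of the outcome SD, with N followed up and m = N/2 per arm:
- Unadjusted, follow-up scores: t(N-2) × sqrt(2/m).
- Unadjusted, change scores (equal SD at both times): the line above × sqrt(2(1-r)).
- Linear model with k covariates: t(N-2-k) × sqrt((2/m) × (1-r²) × (1 + k/(N-k-3))). The last factor is the expected cost of estimating k covariates. k = 1 for baseline only; k = 5 or 6 with trust terms, crediting trust with no outcome variance.

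**Results at N = 38.** sqrt(2/19) = 0.324 and t(36) = 2.028, so the unadjusted follow-up half-width is 0.658.

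| r | Follow-up scores, unadjusted | Change scores, unadjusted | Baseline adjusted | Baseline + 4 / 5 trust terms |
|---|---|---|---|---|
| 0.3 | 0.658 | 0.78 | 0.637 (-3%) | 0.682 / 0.694 |
| 0.5 | 0.658 | 0.66 | 0.579 (-12%) | 0.619 / 0.630 |
| 0.7 | 0.658 | 0.51 | 0.477 (-28%) | 0.510 / 0.520 |
| 0.8 | 0.658 | 0.42 | 0.401 (-39%) | 0.429 / 0.437 |

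Percentages are against 0.658.

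**Break-even r against unadjusted follow-up scores.** At r = 0 the adjusted half-widths are 0.668 (baseline only), 0.715 (four trust terms) and 0.728 (five). Adjustment narrows the interval once r exceeds sqrt(1 - (0.658/0.668)²) = 0.17, sqrt(1 - (0.658/0.715)²) = 0.39 and sqrt(1 - (0.658/0.728)²) = 0.43 respectively.

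**With all 50 analysed.** The unadjusted half-width is 0.569. Baseline adjustment gives 0.498, 0.411 and 0.345 at r = 0.5, 0.7 and 0.8.

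**Chance imbalance.** The SD of the between-arm baseline difference is sqrt(2/25) = 0.28 SD at 25 per arm and sqrt(2/19) = 0.32 SD at 19 per arm. The probability of a gap above 0.3 SD in either direction is 29% and 36% respectively; above 0.5 SD it is 8% and 12%. If follow-up scores are compared, about r times the gap enters the estimate: at r = 0.7 a gap of 0.3 SD contributes 0.7 × 0.3 = 0.21 SD.

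**The case against.** The strongest reply is that this is a feasibility trial. Section 11.1 says clinical differences are not its main purpose, no test is done, and none of the Go/Review/Stop rules in section 4 uses a treatment effect. A simple unadjusted estimate is legitimate and unbiased under randomisation. All of this stands. It limits the importance of the point but does not remove a precision gain that needs no new data.

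Four further objections are partly or wholly right:

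- **Change scores.** If these were meant, the interval is already 0.51 SD at r = 0.7 and 0.42 SD at r = 0.8. Baseline adjustment then gains little, and the model with uninformative trust terms gains nothing. This stands, but the protocol does not say which it means.
- **Trust terms.** They cost degrees of freedom and help only if trusts differ in outcome, which the protocol does not show. This stands. They belong in the model because trust is the stratification factor, not because they promise a gain.
- **Clustering.** A plain linear model ignores CST groups. True, but so does the unadjusted interval. Section 11.1 already foresees work on the intracluster correlation, and this is a separate matter.
- **Residual SD and r.** A reader might infer that the plan cannot supply them for the definitive trial. It can: both time points are collected, so both can be computed whichever contrast is presented.

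A reader might also see a contradiction with section 12.2, where QALYs are adjusted for baseline. That is a different quantity, so there is no contradiction. It shows only that the team accepts baseline adjustment in principle.

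**Conclusion.** The point holds as an improvement in precision, of moderate importance. Against an unadjusted comparison of follow-up scores with 38 people, baseline adjustment narrows the 95% interval by about 3%, 12%, 28% or 39% at r = 0.3, 0.5, 0.7 or 0.8. With trust terms that explain nothing, the model is 4-5% wider at r = 0.3 and then narrower by about 4-6%, 21-22% or 34-35%. The gain therefore comes mainly from the baseline score.

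The result rests on an assumed r, on 75% retention split equally, and on no allowance for clustering by CST group. An r above the break-even values is plausible for the same scales repeated about nine weeks apart, but nothing in the protocol establishes it.

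Stronger readings are not supported. The estimate is not biased or invalid. The protocol does not say that follow-up means are the quantity compared. It gives no basis for saying that most of the follow-up variance exists at baseline, which would need r² above 0.5, or r above 0.71. Nor should the simple efficiency 1/(1-r²), equivalent to 33%, 96% or 178% more participants at r = 0.5, 0.7 or 0.8, be claimed for a model with trust terms: (0.658/half-width)² gives about 9-13%, 60-66% or 127-135%.

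**What to change.** In section 11.1, replace the unadjusted difference as the main estimate. For each continuous outcome, report the mean difference with its 95% confidence interval from a linear model of the follow-up score on arm, baseline score and trust. Keep the unadjusted difference as supplementary, and say whether it compares follow-up or change scores. With the baseline score in the model, the arm effect is the same whichever of the two is the outcome, so the main estimate no longer depends on that choice.

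Report the residual SD and the baseline-to-follow-up correlation for each measure, for use in planning the definitive trial. Handle clustering by CST group through the intracluster correlation work that section 11.1 already foresees.

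The cost is a sentence or two in section 11.1 and matching text in the SAP. No extra participants, visits or data are needed.
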